6.4 Early Termination Visit

The following assessments will be performed at the Early Termination Visit for randomized subjects who are withdrawn from the study prematurely:

- Assess adverse events since the last visit and during this visit
- Assess concomitant medications and medical changes since last visit
- Collect vital signs (pulse, blood pressure, temperature and respiration rate) and height and weight
- Conduct an abbreviated physical examination (including respiratory, cardiovascular, musculoskeletal, gastrointestinal, and dermatological)
- Conduct a biomicroscopy and external eye examination

6.5 Selecting Dosage Strength in Phase 2

The decision of dose strength for P-321 Ophthalmic Solution in Phase 2 of the study will be the responsibility of the Data Review Group constituted by the Principal Investigator (or a designee not directly involved in the conduct of the study), the Medical Monitor and representatives of Parion Sciences. Decision on the dose level to be given in Phase 2 will be made based on unmasked review of the study data from the first 8 subjects by the review committee. Data to be considered will include safety and efficacy measures. A detailed criterion for Dose selection for Phase 2 is described in [Appendix XIV](#) and outlined below.

The dose level may be increased to 0.05% in Phase 2 in the event that:

- 1) No cases of serious, suspected related, unexpected events are noted in Phase 1 OR
- 2) No cases of serious ocular safety events are noted in Phase 1
- 3) Lack of evidence that P-321 produced an increase in tear volume based on OCT and/or Keratograph 5M, or evidence that additional improvements in tear volume (or the duration of effect) may be obtained with a higher dose.

The dose level may be decreased to 0.01% in Phase 2 in the event that:

- 1) No cases of serious, suspected related, unexpected events are noted in Phase 1
- 2) No cases of serious ocular safety events are noted in Phase 1
- 3) There is evidence of a significant increase in tear volume and the duration of effect based on OCT and/or Keratograph 5M

The dose level may remain at 0.017% (the same as in Phase 1) in the event:

- 1) No cases of serious, suspected related, unexpected events are noted in Phase 1
- 2) No cases of serious ocular safety events are noted in Phase 1
- 3) There is not compelling data to either increase or decrease the strength for Phase 2.

The Data Review Group will make a recommendation to Parion Sciences to increase the dose, decrease the dose or maintain the dose.

Additional unmasked reviews of subject data may occur throughout the study to make recommendations on further dose adjustments and for planning purposes. These reviews will follow the procedures outlined above.

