7.3 Methods to Minimize Bias

To minimize bias, the treatment regimen will be randomized and masked. The randomization code will be generated by an independent designee of Parion Sciences, Inc. who is not involved in the day-to-day conduct of the clinical study. The randomization code will be provided to the designee of Parion Sciences, Inc. who is responsible for the manufacture, packaging and labeling

of the clinical supplies; further the randomization code will be maintained in a secure location separate from the clinical study site personnel.

The Medical Monitor and Principal Investigator and members of the Parion team not involved in the conduct of the study will be unmasked as part of the Data Review Group for decision making on the strength of P-321 Ophthalmic Solution to be used in Phase 2 of the study. The treatment assignments will remain masked to subjects in the study, the clinical monitor, and other site and Parion Sciences personnel involved in the conduct of the study and not involved in the Data Review Group. Additional unmasked reviews of subject data may occur throughout the study to make recommendations on further dose adjustments and for planning purposes. These reviews will follow the procedures outlined in [Section 6.5](#).

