APPENDIX XIV: DOSE SELECTION FOR PHASE 2 AND DATA REVIEW DURING STUDY

The decision on dosage strength to be used in Phase 2 will be the responsibility of the Data Review Group constituted by the Principal Investigator (or designee), Medical Monitor and representative(s) of Parion Sciences not involved in the conduct of the study. The Data Review Group may request the participation of an independent statistician to assist in the assessment of the safety of the study medication and the dosage strength selection for Phase 2.

The Data Review Group will review unmasked data in order to make a decision on the dose to be administered in Phase 2. The Data Review Group will convene when approximately 8 subjects have completed the study, or earlier if needed. The trial will continue enrolling during the time the review by the Data Review Group is being prepared and being held. The Data Review Group will review the following to assist in making their recommendation for dose selection in Phase 2:

- Adverse events
- Biomicroscopy and external eye examination
- Drop instillation comfort assessments
- Abnormal alert laboratory results
- Tear volume via OCT
- Tear volume via Keratograph 5M

Recommendations by the Data Review Group may include:

- 1) The dose level may be increased to 0.05% in Phase 2 in the event that:
 - a) No cases of serious, suspected related, unexpected events are noted in Phase 1 AND
 - b) No cases of serious ocular safety events are noted in Phase 1
 - c) Lack of evidence that P-321 produced an increase in tear volume based on OCT and/or Keratograph 5M, or evidence that additional improvements in tear volume (or the duration of effect) may be obtained with a higher dose
- 2) The dose level may be decreased to 0.01% in Phase 2 in the event that:
 - a) There is evidence of a significant increase in tear volume and duration of effect in Phase 1 based on OCT and/or Keratograph 5M
 - b) No cases of serious, suspected related, unexpected events are noted in Phase 1
 - c) No cases of serious ocular safety events are noted in Phase 1
- 3) The dose level may remain at 0.017% (the same as in Phase 1) in the event that:
 - a) There is no compelling data to either increase or decrease the strength for Phase 2.
 - b) No cases of serious, suspected related, unexpected events are noted in Phase 1
 - c) No cases of serious ocular safety events are noted in Phase 1
- 4) Discontinue the study.
- 5) Amend the protocol

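### Section 6.5 lets the dose rise to 0.05% if either of two safety conditions holds, while Appendix XIV requires both

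*Combined protocol and SAP*

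**What the plan says.** Section 6.5 introduces its dose rules as an outline of Appendix XIV: "A detailed criterion for Dose selection for Phase 2 is described in" that appendix. It then gives three conditions for raising the dose to 0.05%. The first reads "No cases of serious, suspected related, unexpected events are noted in Phase 1 OR", the second is that no serious ocular event occurred in Phase 1, and the third concerns tear volume. No connective stands before the third.

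Appendix XIV lists the same three conditions, but the first reads "No cases of serious, suspected related, unexpected events are noted in Phase 1 AND". It too has no connective before the tear-volume condition.

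The other two rules in Section 6.5 ("The dose level may be decreased to 0.01% in Phase 2 in the event that" and "The dose level may remain at 0.017% (the same as in Phase 1) in the event") list both safety conditions with no OR, and Appendix XIV does the same. Section 6.5 closes with three possible outcomes: "The Data Review Group will make a recommendation to Parion Sciences to increase the dose, decrease the dose or maintain the dose". Appendix XIV adds two more, "Discontinue the study" and amending the protocol.

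On later unmasked reviews, Sections 7.3, 7.7 and 8.1.5 each say "These reviews will follow the procedures outlined in" Section 6.5. The paragraph on additional reviews in Appendix XIV refers instead to the appendix's own procedures.

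**The concern.** A rule for escalating dose should have one reading. Here the summary in the body and the detailed rule in the appendix differ on whether one satisfied safety condition is enough, and no clause states which prevails. Read literally, Section 6.5 also sets a weaker safety bar for raising the dose than for keeping or lowering it, which cannot be what was meant.

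The ocular condition matters most at this strength. Section 2.2.3 calls ocular irritation the dose-limiting factor and gives a no-effect level in dogs of 0.024 mg/eye/day. With the 40 µl drop assumed there, 0.05% delivers 0.5 mg/ml × 0.04 ml = 0.02 mg per eye, so the margin is 0.024 / 0.02 = 1.2-fold. That is the low end of the range in Section 2.4. The completed human study (Section 2.3) went no higher than 0.01%, although twice daily for up to 28 days. Under OR, a serious ocular event does not by itself block the step to 0.05%.

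**Working it through.** The plan gives no figure to reproduce on this point. The check compares the two rules over every combination of their conditions.

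**Inputs** (Section 6.5 and Appendix XIV, current version)

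- A: no serious event in Phase 1 that is both suspected related and unexpected
- B: no serious ocular event in Phase 1
- C: the tear-volume condition for an increase is met

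**Rules**

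- Section 6.5, natural reading: increase allowed if (A or B) and C
- Appendix XIV: increase allowed if A and B and C
- Hold and lower rules, both texts: each needs A and B, reading lists without connectives as requiring every item

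| A | B | C | Section 6.5 increase | Appendix XIV increase | Safety conditions for hold or lower met |
|---|---|---|---|---|---|
| yes | yes | yes | allowed | allowed | yes |
| yes | yes | no | not allowed | not allowed | yes |
| yes | no | yes | **allowed** | **not allowed** | no |
| yes | no | no | not allowed | not allowed | no |
| no | yes | yes | **allowed** | **not allowed** | no |
| no | yes | no | not allowed | not allowed | no |
| no | no | yes | not allowed | not allowed | no |
| no | no | no | not allowed | not allowed | no |

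The texts disagree in 2 of 8 rows.

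- Row 3 is a serious ocular event judged unrelated or expected, with no other event failing A.
- Row 5 is a non-ocular serious event that is suspected related and unexpected, with no serious ocular event.

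In both rows the hold and lower rules are closed, so an increase is the only one of Section 6.5's three outcomes whose stated conditions are satisfied. A serious ocular event that is also suspected related and unexpected falls in the last two rows, where both texts bar the increase.

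**Alternative reading.** Because Section 6.5 has no connective before its third condition, it could be parsed as A or (B and C). That differs from Appendix XIV at (A, B, C) = (yes, yes, no), (yes, no, yes), (yes, no, no) and (no, yes, yes), which is 4 of 8.

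**After correction.** With AND in place of OR, Section 6.5 becomes A and B and C and agrees with Appendix XIV in 8 of 8 rows.

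**Origin.** Version 1.0, in the same file, has the same OR in its Section 6.5 and the same AND in its Appendix XIV. The mismatch was carried into the current version.

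**The case against.** The best defence is that Section 6.5 presents itself as an outline and sends the reader to Appendix XIV for the detail, so a careful group would follow the appendix. The rules say only that the dose may change, never that it must, and Appendix XIV also offers stopping or amending. Sections 5.5 and 8.5 allow termination at any time, and the sponsor takes the final decision with subjects' interests in view. Section 2.3 reports no serious adverse events in the earlier study of 40 treated subjects, although at strengths up to 0.01%. The conflict therefore needs a serious event of a particular kind among about 8 subjects, and then a group that prefers the outline to the detail. Counting logical combinations says nothing about how often this would happen. The 4-of-8 parsing is strained, since it would allow escalation with no tear-volume reason.

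Most of this stands as a limit on the consequences. The counts are not probabilities, and the 4-of-8 figure is secondary. The contradiction remains, however. The outline is the text to which Sections 7.3, 7.7 and 8.1.5 direct later reviews, and a group could follow either text and claim compliance. The point that only an increase stays open relies on reading all three permissive rules in the same way, which is the natural way to read parallel lists. A safety gate should not rely on its users to correct its wording.

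**Conclusion.** The concern holds and should be fixed. Section 6.5 and Appendix XIV state different safety conditions for escalation to 0.05%, and they conflict in 2 of 8 combinations under the natural reading. This rests on reading the unconnected lists as requiring every item and on treating the tear-volume condition as necessary for an increase. The documents give no expected rate for such events, so no probability is attached. The parallel hold and lower rules make it clear that AND was meant. This is a drafting error in an operative safety rule; it does not affect the sample size or the analysis.

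**What to change.** In Section 6.5, change OR to AND between the first and second conditions for an increase. This is the essential step, and it removes the disagreement.

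Two further edits close the remaining gaps. Write AND before the tear-volume condition in both Section 6.5 and Appendix XIV, which rules out the alternative parsing. State in Sections 6.5, 7.3, 7.7 and 8.1.5 that Appendix XIV controls dose decisions.

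The cost is a short amendment covering three connectives and four cross-references. Under Section 13.1 it needs ethics approval before it takes effect. Visits, sample size and analysis are unchanged.

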2.2.3 Toxicology

Multiple toxicology studies have been conducted using P-321 Ophthalmic Solution. Systemic administration of P-321 via IV, oral and ocular routes of administration, in both acute and repeat-dose nonclinical studies, demonstrated that P-321 Ophthalmic Solution at pharmacologically active concentrations is well tolerated. Extensive ocular toxicology studies for up to 28 days of administration at higher frequencies than those used in this study have been conducted in rabbits and dogs, with the dog being the most sensitive species. The primary finding associated with ocular administration of P-321 was a dose-dependent increase of ocular irritation, described as minimal or slight, that reversed upon discontinuation of treatment. No significant effects of P-321 Ophthalmic Solution were observed at any dose level for both species on electroretinograms, corneal thickness, and corneal endothelial cell density. For the dose limiting factor of ocular irritation, the no-observed-adverse-effect levels (NOAEL) of 0.8 mg/eye/day in rabbits and 0.024 mg/eye/day in dogs exceeds the human doses planned for this study. The NOAEL of 0.05 mg/kg/day in rats administered P-321 IV exceeds the potential exposure from

the proposed initial ocular dose of 2.2661×10^{-4} mg/kg/day (assuming bilateral dosing of 0.017% P-321, QD with a 40 μ l drop size in a 60 kg person) by 225-fold on a Human Equivalent Dose basis. For the high dose planned in this study, the dose of 6.666×10^{-4} mg/Kg/day (assuming bilateral dose of 0.05% P-321 QD in a 60 Kg person, the systemic safety margin is 75-fold on a Human Equivalent Dose basis.

No systemic effects at any dose level in dogs or rabbits were observed following ocular administration of P-321 Ophthalmic Solution.

In a battery of genotoxicity studies, P-321 did not cause mutations in the Ames or mouse lymphoma assay in vitro with or without S9 metabolic activation. Additionally, the compound was negative in a rat micronucleus study. Thus, P-321 can be considered to be non-mutagenic and non-clastogenic, with no evidence of disruption of the mitotic apparatus.

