7.7 Maintenance of Randomization and Procedure for Breaking the Code

The treatment assignments will be masked to the investigator, medical monitor, study site personnel, subjects in the study and those involved in the conduct of the study.

Only in the case of a medical emergency, or occurrence of a suspected related, unexpected, SAE, may the randomization code be unmasked and made available to the investigator, medical monitor, subject, and/or other personnel involved in the monitoring or conduct of this study. In the absence of medical need, the randomization code will not be available to the above personnel until after the study is completed and the database is locked.

The Data Review Group will review unmasked data. The Medical Monitor and Principal Investigator (or designee) and members of the Parion team not involved in the conduct of the study will be unmasked as part of the Data Review Group for decision making on the strength of P-321 Ophthalmic Solution to be used in Phase 2 of the study. The treatment assignments will remain masked to subjects in the study, the clinical monitor, and other site and Parion Sciences personnel involved in the conduct of the study and not involved in the Data Review Group. Additional unmasked reviews of subject data may occur throughout the study to make recommendations on further dose adjustments and for planning purposes. These reviews will follow the procedures outlined in [Section 6.5](#).

For Phase 1, a randomization list will be generated and the kits will be labeled in a masked fashion. The randomization assignments will be kept in a secure area at Parion Sciences, Inc. or designee. For Phase 2, a randomization list will be provided to the pharmacy and the pharmacy will distribute the assigned drug according to the randomization schedule with subjects remaining masked.

In case of a medical need, the investigator will treat the subject as needed regardless of randomized treatment. Since there is no specific antidote to P-321 Ophthalmic Solution, immediate emergency unmasking is not necessary. If the investigator feels it is necessary to unmask a subject's treatment assignment after an emergency situation, the investigator must call the medical monitor and notify Parion Sciences, Inc. The treatment assignment will be revealed on a subject-by-subject basis, leaving the masking of the remaining subjects intact.

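### For escalation to 0.05%, Section 6.5 joins the two Phase 1 safety conditions with OR where Appendix XIV joins them with AND

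*Combined protocol and SAP*

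**What the plan says.** The Data Review Group chooses the Phase 2 dose after an unmasked review of about 8 Phase 1 subjects. The current protocol states the rule for an increase to 0.05% twice.

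- **Section 6.5.** Condition 1 is "No cases of serious, suspected related, unexpected events are noted in Phase 1 OR". Condition 2 is the absence of any serious ocular safety event in Phase 1. Condition 3 concerns tear volume: either no sign that P-321 raised it, or signs that a higher dose could add to the effect or its duration.
- **Appendix XIV.** The same three conditions appear, but the first reads "No cases of serious, suspected related, unexpected events are noted in Phase 1 AND".

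Section 6.5 presents itself as a summary of the appendix: "A detailed criterion for Dose selection for Phase 2 is described in" Appendix XIV, with an outline to follow. In both places the maintain and decrease options list the same two safety conditions, without an OR.

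The lists of possible recommendations differ in length. Section 6.5 ends with "The Data Review Group will make a recommendation to Parion Sciences to increase the dose, decrease the dose or maintain the dose". Appendix XIV has these three and two more: "Discontinue the study", and amending the protocol.

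On later looks at the data, Section 7.3 says: "Additional unmasked reviews of subject data may occur throughout the study to make recommendations on further dose adjustments and for planning purposes". Sections 7.3, 7.7 and 8.1.5 direct those reviews to Section 6.5 ("These reviews will follow the procedures outlined in" that section), and Section 6.5 points them to its own text. Appendix XIV has its own paragraph on additional reviews, which points them to the appendix.

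**The concern.** Two passages meant to state one rule give different answers to the same question: may the dose be raised after a serious event in Phase 1? Under AND, either kind of event rules out the increase. Under OR, the increase is ruled out only if both conditions are breached. A member of the Data Review Group working from Section 6.5 could regard escalation as allowed by the protocol after a breach that, for a colleague working from Appendix XIV, forbids it.

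The rule governs the only upward dose step in the trial, from 0.017% to 0.05%. It is an operative safety criterion, so its logical connective should not depend on which page is open.

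**Working it through.** The plan gives no figure to reproduce here. The check sets the two rules side by side and enumerates the cases.

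**Inputs** (Section 6.5 and Appendix XIV):

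- A = no serious, suspected related, unexpected event in Phase 1
- B = no serious ocular safety event in Phase 1
- C = the tear-volume condition

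**Rules for the increase:**

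- Section 6.5: (A OR B) AND C
- Appendix XIV: A AND B AND C

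Neither text puts a connective before C. I read it as required in both.

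**Rules for maintain and decrease in Section 6.5:** A and B are listed with no connective. I read both as required, each together with that option's own tear-volume condition.

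**Safety states, with C met:**

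| A | B | Example | Increase, Section 6.5 | Increase, Appendix XIV | Safety conditions for maintain or decrease, Section 6.5 |
|---|---|---|---|---|---|
| holds | holds | no such event | open | open | met |
| holds | breached | serious ocular event judged unrelated or expected | open | closed | not met |
| breached | holds | non-ocular serious, suspected related, unexpected event | open | closed | not met |
| breached | breached | serious ocular event that is suspected related and unexpected | closed | closed | not met |

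**Counts.** The increase is open in 3 of 4 states under Section 6.5 and in 1 of 4 under Appendix XIV. They disagree in 3 − 1 = 2 of 4, and Section 6.5 is the looser text each time. If C is not met, both rules are closed, so over all 8 combinations of A, B and C the disagreement is still those 2.

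**An internal sign of the slip.** In the two disagreeing rows, the increase is the only one of the three dose options in Section 6.5 that remains open. After a serious event the dose could go up but could neither stay nor come down. No drafter would intend that ordering.

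**After changing OR to AND.** The two rules agree in 4 of 4 states. All three dose options in Section 6.5 then need both A and B, so in 4 − 1 = 3 of 4 safety states Section 6.5 on its own lists no outcome. Appendix XIV does list outcomes for those states: discontinue or amend.

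**The case against.** The strongest reply is that nobody would act on the OR. Section 6.5 names Appendix XIV as the place of the detailed criterion, its own maintain and decrease lists contradict the literal reading, every option is worded as something the group may do, and Appendix XIV requires the sponsor's decision to protect subjects' interests. All of this stands, and it makes a wrong escalation unlikely. It does not remove the contradiction: no sentence says which text prevails. Nor is OR an artefact of text extraction, since the superseded protocol version in the same file has the same OR and AND in the same places.

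A reader might infer more than the documents support, in four ways.

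- **That later reviews are governed by the OR text alone.** They are not. Sections 6.5, 7.3, 7.7 and 8.1.5 lead to Section 6.5, but the appendix's own paragraph leads the same reviews to the AND text. The routing goes to both.
- **That the known toxicity is what slips through.** Section 2.2.3 reports that "The primary finding associated with ocular administration of P-321 was a dose-dependent increase of ocular irritation". But a serious irritation event caused by the drug would presumably be suspected related. Findings so far were minimal or slight (Section 2.2.3), and the one completed human study reported no serious adverse event (Section 2.3), so it would probably also count as unexpected. It would then breach both conditions, and both texts would forbid the increase. This is inference, because the reference that sets expectedness is not among these documents.
- **That the protocol lacks a way to stop.** Sections 5.5 and 8.5 and Appendix XIV all provide one. The shorter list in Section 6.5 belongs to an outline and is not a separate defect.
- **That OR splits condition 1 from conditions 2 and 3 together.** That reading would allow escalation with no tear-volume reason at all, which is implausible.

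**Conclusion.** Wrong as written. Section 6.5 and Appendix XIV state the same escalation rule with opposite connectives, and they disagree in 2 of 4 safety states when the tear-volume condition is met. These are counts of logical cases, not probabilities. The trigger is expected to be rare.

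The count rests on two reading assumptions: the tear-volume condition is required in both texts, and safety conditions listed without a connective are all required. The conclusion that Section 6.5 should say AND does not depend on the count. It follows from Section 6.5 describing itself as an outline of Appendix XIV. The practical risk is small, but a dose-escalation safety criterion should not contradict itself, so the correction should be made.

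**What to change.** In Section 6.5, under the increase to 0.05%, change OR to AND after the first condition.

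As a conforming edit only, add discontinuing the study and amending the protocol to the recommendations in Section 6.5, as in Appendix XIV. Section 6.5 then lists an outcome when a safety condition has been breached.

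The cost is one word and two list items, with no effect on design, sample size, schedule or analysis.
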